#### 4.1.1. Handling of Immunogenicity Data

Immunogenicity data are log-normally distributed and will be presented using n, geometric means and corresponding 95% confidence intervals (CI), median, minimum, and maximum. Figures for immunogenicity data will be scaled using a logarithmic y-axis.

Neutralizing antibody results for the index virus and any VOCs with World Health Organization (WHO) normalized units at the time of analysis will be scaled to WHO standard units (IU/mL). Neutralizing antibody results for the VOCs without WHO normalized units will be summarized as titer values. For all neutralizing antibody results, values below the lower limit of detection (LLOD) will be given a value of half of the LLOD. Values that are below the LLOQ but at or above the LLOD will be analyzed as half of the value of the LLOQ.

Total antibody results measured by ELISA will also be scaled to WHO standard units (BAU/mL). Values below the LLOQ will be given a value of half of the LLOQ.

ELISpot results will be presented in spot forming units (SFUs)/10^6 PBMCs. Interferon- $\gamma$  and interleukin-4 results will be summarized separately within individual stimulant pools. Values below the LLOD will be given a value of half of the LLOD. Values that are below the LLOQ but at or above the LLOD will be analyzed as half of the value of the LLOQ. Values above the upper limit of quantitation (ULOQ) will be given a value of twice the ULOQ.

#### 4.1.2. Handling of Missing Data

All data will be listed and summarized as captured in the eCRF or transferred from external sources (e.g., central lab results, immunogenicity results, protocol deviations).

It may be necessary to impute incomplete AE and medication start and end dates to assign these events to the correct trial phase. For prior and concomitant medications, as well as AEs, imputation of partial start and end dates will be done for analysis purposes according to the following rules:

**Table 4: Adverse Event and Concomitant Medication Date Imputation Rules**

Missing	Rule for Start Date a	Rule for End Date b	Flag for Imputation c
Day	First of month	Last of month	D
Month	1 January	31 December	M
Year	No imputation	Last visit date	Y

a If the imputed start date is before the trial vaccination date, the trial vaccination date is used to be conservative.

b If the imputed end date is after last visit date, the last visit date available is used to be conservative.

c It is assumed that a missing month implies a missing day as well, and that a missing year implies a missing month and day.

If the imputation of a partial start date of an AE leads to a start date prior to the date of trial vaccination, it will be set to the date of trial vaccination and assigned to be on treatment and in the Active Trial Phase, to be conservative. Original date values as collected will be presented in listings.

For AEs and medications with partial or missing start and/or stop dates, the “worst case” should be applied to be conservative. Therefore, the following rules will apply:

#### AEs

- If start date is partial and any portion (i.e., year or month and year) would confirm the AE was prior to trial vaccination, the AE will be considered a Baseline Sign or Symptom.
- If the start date is completely missing and the end date, or any portion of a partial end date, confirms the AE ended prior to trial vaccination, the AE will be considered a Baseline Sign or Symptom.
- Otherwise, the AE will be considered as belonging to the Active Trial Phase.

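### SAP 4.1.2 can place adverse events with incomplete dates in the wrong trial phase: two rules conflict before vaccination, and there is no branch for onsets known to be in follow-up

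*SAP*

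**What the plan says.** SAP 4.1.2 gives the purpose of date imputation: "It may be necessary to impute incomplete AE and medication start and end dates to assign these events to the correct trial phase". Table 4 then imputes a start date with the day missing as "First of month", and one with the month missing as 1 January.

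Two sets of rules follow.

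- **The reset.** Table 4 note a: "If the imputed start date is before the trial vaccination date, the trial vaccination date is used to be conservative". The text below the table repeats this for adverse events: "If the imputation of a partial start date of an AE leads to a start date prior to the date of trial vaccination", then "it will be set to the date of trial vaccination and assigned to be on treatment and in the Active Trial Phase". It makes no exception for a start whose known month or year is already earlier than vaccination.
- **The AE bullets.** These are introduced as covering partial or missing start and/or stop dates. Bullet 1 begins "If start date is partial and any portion (i.e., year or month and year) would confirm the AE was prior to trial vaccination" and makes such an event a Baseline Sign or Symptom. Bullet 2 does the same when the start is wholly missing and the end date confirms that the event was over before vaccination. The last bullet is the remainder: "Otherwise, the AE will be considered as belonging to the Active Trial Phase".

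SAP 4.1.5 counts safety information collected within 35 days of vaccination as Active Trial Phase and defines a separate Follow-up Phase from the EAP visit onward. SAP 4.5.2.6 plans AE summaries for the entire trial, the Active Trial Phase and the Follow-up Phase. Protocol 5.3 lists SAEs, AESIs or MAAEs in the active phase as one safety endpoint, and the same events over the entire trial as another.

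**The concern.** An event whose known month or year is wholly before vaccination always imputes to before vaccination. It therefore always meets both the reset and bullet 1, which give different answers. The SAP states no precedence, so the programmer has to choose.

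An event whose known month is wholly past the active phase meets neither baseline bullet, so it falls to the remainder bullet and is labelled Active. It then carries an imputed follow-up date under Table 4 and an active-phase label under the bullets, which defeats the stated purpose of the imputation.

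The second defect falls on endpoint events. Apart from active-phase AEs not yet resolved, follow-up data collection is limited to SAEs, AESIs and MAAEs (Trial Schedule, note h), and AESIs include confirmed COVID-19 (Protocol 11.9.1). These are the categories counted in the active-phase endpoint. Part B has no comparator against which a shifted rate could be read.

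**Working it through.** The plan states no figure to reproduce here, so the check applies both sets of rules to the same records.

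**Example.** Vaccination on 5 October 2022 (an illustrative date), only the day of onset missing, Table 4 imputing to the first of the month. Days from vaccination: 1 November = 26 + 1 = 27; 1 December = 27 + 30 = 57; 1 January = 57 + 31 = 88; 1 February = 88 + 31 = 119. Going back, 1 October is 4 days before and 1 September is 30 + 4 = 34 days before.

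| Recorded onset | Imputed start, days from vaccination | Phase by imputed date, reset and 35-day limit | Phase by AE bullets |
|---|---|---|---|
| Sep 2022 | −34 | Active (reset) | Baseline |
| Oct 2022 | −4 | Active (reset) | Active |
| Nov 2022 | 27 | Active | Active |
| Dec 2022 | 57 | Follow-up | Active |
| Jan 2023 | 88 | Follow-up | Active |
| Feb 2023 | 119 | Follow-up | Active |

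The two routes disagree in the first row and in the last three.

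**How often a day-missing record meets each defect.** This counts over every vaccination date in one year, assuming onset uniform over the stated days.

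- *Before vaccination.* Screening lasts at most 14 days (Protocol 8.1). An onset k days before vaccination falls in an earlier month for 12k of 365 vaccination dates. The mean of k over 1 to 14 is 7.5, so the share is 12 × 7.5 / 365 = 0.247, about 25%.
- *Follow-up.* For onsets on days 36 to 196 (the end of the FU3 window), direct counting gives 0.909: about 91% have a month that starts more than 35 days after vaccination, yet the bullets make them Active. If only the year is known, the share is about 22%.

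**Possible effect on active-phase counts.** Let A and F be the true numbers of active-phase and follow-up events, and q the share of follow-up events lacking only the day. The relative inflation of the active count is q × 0.909 × F/A. The documents give neither q nor F/A, so both are assumptions.

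| q | F/A = 1 | F/A = 2 |
|---|---|---|
| 1% | 0.9% | 1.8% |
| 5% | 4.5% | 9.1% |
| 10% | 9.1% | 18.2% |

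**Missing stop dates.** The introductory wording also covers events with only the stop date incomplete. An event with a complete start date in follow-up and no stop date meets neither bullet 1 (which needs a partial start) nor bullet 2 (which needs a missing start). Read literally, it also goes to the Active Trial Phase.

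**The case against.** The SAP openly takes a worst-case approach in order to be conservative, and it keeps the collected dates in listings. That defends placing an undetermined onset in the active phase. It does not defend doing so when the known month rules that phase out, because the event is then also removed from the follow-up summary. Listings do not correct tables.

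Incomplete onset dates should be uncommon for these events. SAEs and AESIs must be entered within 24 hours of awareness, with date of onset in the minimum report (Protocol 11.14.1). MAAEs have the same 24-hour limit (Protocol 11.14.2), and queries are resolved before lock (SAP 4.7). This stands, and it limits the size.

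The pre-vaccination conflict is narrow. Screening is short, and AESIs and MAAEs are not collected until vaccine is received (Trial Schedule, note g). Within the SAE/AESI/MAAE endpoint, only a screening-period SAE could be moved. There is also a sensible reading in which the reset serves dates in the month of vaccination and the more specific bullet governs confirmed earlier onsets. The SAP does not say so, but one sentence would settle it.

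Safety is summarized descriptively (Protocol 12.9), and in Part A the same rules apply to both arms. Both points stand. It might be added that the primary analysis uses data only to the 8-week contact, so a February example lies beyond it. The December row, which imputes to day 57, shows that the defect can arise within that data cut too, and the later analyses use the same rules.

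A reader might also infer that giving a long-standing medication the vaccination date as its start distorts the medication tables. The documents do not support this. Prior or concomitant status depends on the end date (SAP 4.1.2, 4.1.5 and 4.6.5), and no planned medication table uses the start date.

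**Conclusion.** Both textual defects are real. For confirmed pre-vaccination onsets the SAP gives two answers without precedence. For onsets known to lie beyond the active phase it gives a wrong one. The second matters more, because it bears on a listed safety endpoint. Its direction is known: active-phase counts too high, follow-up counts too low.

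A reader might conclude that the phase-specific safety counts are wrong. The documents do not support that. Only events with incomplete dates are affected; their number is not given and is probably small. A swap between Active and Follow-up leaves the entire-trial endpoints unchanged. The only route to an extra entire-trial event is the pre-vaccination conflict, if the reset is applied to an event known to have started during screening.

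The 25%, 91% and 22% shares rest on uniform onset, and the inflation table rests on assumed values of q and F/A. They show how the rule behaves and do not estimate what happened in this trial. The point does not touch the immunogenicity analyses. The rules should be corrected because they are explicit and would be programmed as written.

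**What to change.** In SAP 4.1.2, apply the AE bullets only to events with an incomplete start date. Classify events with a complete start date by that date under SAP 4.1.5, whatever the state of the stop date. Then apply, in this order:

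1. If the known parts of the start date, or the end date when the start is wholly missing, confirm that the event was before vaccination, it is a Baseline Sign or Symptom. This keeps bullets 1 and 2 and overrides the reset.
2. If the earliest date compatible with the known parts of the start is more than 35 days after vaccination, the event belongs to the Follow-up Phase.
3. Only an onset left undetermined goes to the Active Trial Phase, and for AEs the reset in Table 4 note a and the text below it is limited to these events.

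The medication rules need no change for this purpose. The cost is a few lines of SAP text and one derivation, with no new data. A count of AEs with incomplete start dates, by phase assigned, would show readers of the report how much the rule mattered.

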#### Medications

- If the end date is partial, and any portion confirms the medication was ended prior to trial vaccination, the medication will be considered a Prior Medication.
- Otherwise, the medication will be considered a Concomitant Medication.

Missing data imputation for immunogenicity data as a sensitivity analysis of the primary endpoint is described in Section 4.2.3.1.

### 4.1.3. Unblinding

Unblinding for Part A reporting will happen after the lock for the primary analysis (see Section 4.7). After unblinding for the primary analyses, the operational team will remain blinded on individual subject level until the follow-up phase of Part A of the trial is completed. Bavarian

Nordic team members unblinded at the subject level will no longer support the blinded team operation during the follow-up phase.

#### 4.1.4. Baseline

Baseline is defined as the last available measure prior to trial vaccination. Baseline values may come from the screening, vaccination visit, or an unscheduled visit prior to the trial vaccination visit. If multiple pre-vaccination values are available, the one closest in time to the trial vaccination will be used as the baseline value. If no time is collected for a value measured on the date of trial vaccination, measurements required to be collected prior to vaccination per the clinical trial protocol will still be considered eligible for inclusion as baseline measurements. Subjects missing baseline values will not be included in analyses of the change/shift from baseline or ratio to baseline.

Note, as the primary endpoint and analysis for the trial does not require a baseline measurement, but rather a week 2 neutralizing antibody result for the index virus, subjects missing a baseline value are not excluded from the IAS. These subjects will, however, be excluded from analyses presenting geometric mean fold increases from baseline.

#### 4.1.5. Trial Phase and Windowing

The following trial phases are defined for this trial:

**Screening Phase:** The phase from the subject's signing of informed consent to the trial through the date and time of trial vaccination. AEs collected during the Screening Phase are considered Baseline Signs and Symptoms and are included as Medical History events in the SDTM database.

**Active Trial Phase:** The phase from the trial vaccination up to and including the week 4 End of Active Phase (EAP) Visit (28-35 days after vaccination). In the event of early withdrawal of a subject from the trial during the Active Trial Phase, the EAP Visit may occur prior to the scheduled EAP Visit window. For safety analyses, any safety information collected within 35 days of trial vaccination will be included in summaries of the Active Trial Phase.

**Follow-up Phase:** The phase from the EAP Visit through the final FU visit. Subjects have 3 FU visits scheduled per protocol at Weeks 8 (phone), 13, and 26. Subjects may withdraw from the Active Trial Phase early but continue into the FU Phase. Completion of the trial requires all follow-up visits to be attended and can be achieved even if the Active Trial Phase is discontinued early.

For assigning prior and concomitant medications, those ending prior to trial vaccination are considered prior medications. All other medications are considered concomitant medications.

Per protocol, all visits are to occur within the specified window in the schedule of events (Appendix 1). For sensitivity analyses, immunogenicity samples taken out of window will be handled as described in Section 4.2.3.1.

In general, safety analyses will be performed by trial phase. The Active Trial Phase summaries will account for any observations between the vaccination and the EAP visit, inclusive of the EAP visit and any unscheduled visits during this phase. Nominal visits will be used for the

summaries by visit, with the worst/highest toxicity grade value presented for the visit in the case of multiple reported observations.

#### 4.1.6. Baseline Comorbidities

Baseline comorbidities include underlying conditions that increase the risk of severe COVID-19. The following list of conditions are based on the Center for Disease Control and Prevention’s Underlying Medical Conditions Associated with Higher Risk for Severe COVID-19: Information for Healthcare Professionals (<https://www.cdc.gov/coronavirus/2019-ncov/hcp/clinical-care/underlyingconditions.html>), in which the CDC determined the conditions to be conclusive of higher risk of severe COVID-19. The following table includes how the conditions will be identified from the medical history and baseline signs and symptoms collected for each subject as coded according to the Medical Dictionary for Regulatory Activities (MedDRA).

**Table 5: Baseline Comorbidity Definitions**

Condition	MedDRA Definition
Asthma, Bronchiectasis, COPD	High Level Term : Bronchospasm and obstruction Preferred Term : Bronchiectasis
Cancer	System Organ Class + High Level Group Term : “Neoplasms benign, malignant and unspecified (incl cysts and polyps)” AND High Level Group Term includes “malignant” Preferred Terms : Cancer surgery Hodgkin's disease Non-Hodgkin's lymphoma
Cerebrovascular disease	High Level Group Term : Central nervous system vascular disorders Aneurysms and artery dissections ( please exclude PTs Aneurysm and Peripheral artery aneurysm ) High Level Terms : Arterial therapeutic procedures (excl aortic) ( please exclude PTs Patent ductus arteriosus repair and Renal artery stent placement ) Preferred Terms : Aortic arteriosclerosis Arteriosclerosis Intermittent claudication Peripheral arterial occlusive disease
Chronic kidney disease	High Level Term : Renal failure and impairment Preferred Terms : Nephropathy Hypertensive nephropathy
Chronic liver disease (cirrhosis, non-alcoholic fatty liver disease, alcoholic liver disease, autoimmune hepatitis)	High Level Terms : Hepatic fibrosis and cirrhosis Hepatocellular damage and hepatitis NEC
Cystic fibrosis	Preferred Term : Cystic fibrosis
Diabetes mellitus, type 1 and type 2	High Level Term : Diabetes mellitus (incl subtypes) Preferred Term : Diabetic neuropathy

Condition	MedDRA Definition
Disabilities, including Down Syndrome	High Level Term: Disability issues Preferred Term: Congenital foot malformation
HIV	Excluded from trial
Heart conditions (such as heart failure, coronary artery disease, or cardiomyopathies)	High Level Group Term: Cardiac therapeutic procedures ( please exclude PTs Left atrial appendage closure implant, Cardiac operation, Atrial septal defect repair ) High Level Terms: Cardiac disorders NEC Cardiac disorders congenital NEC Aortic valvular disorders Cardiac valve disorders NEC Mitral valvular disorders Pulmonary valvular disorders Coronary artery disorders NEC Ischaemic coronary artery disorders Heart failures NEC Cardiomyopathies Myocardial disorders NEC Preferred Terms: Ventricular fibrillation
Interstitial lung disease	High Level Term: Parenchymal lung disorders NEC
Mental health conditions (such as mood disorders, including depression, and schizophrenia spectrum disorders)	High Level Terms: Adjustment disorders Depressive disorders Mood alterations with depressive symptoms Pervasive developmental disorders NEC Hallucinations (excl sleep-related) Bipolar disorders Fluctuating mood symptoms Mood disorders NEC Psychotic disorder NEC Schizoaffective and schizophreniform disorders Schizophrenia NEC
Neurologic conditions (including Dementia)	High Level Terms: Dementia (excl Alzheimer's type) Dementia NEC Alzheimer's disease (incl subtypes) Central nervous system disorders congenital NEC Preferred Term: Cerebral palsy Paraplegia
Obesity	Preferred Terms: Central obesity Obesity Vital Signs: Baseline BMI of $\geq 30$
Physical Inactivity	Not collected as a baseline variable
Pregnancy and Recent Pregnancy	Excluded from trial

Condition	MedDRA Definition
Primary Immunodeficiencies	Excluded from trial
Pulmonary hypertension and pulmonary embolism	High Level Terms: Pulmonary hypertensions Pulmonary thrombotic and embolic conditions
Smoking, current and former	High Level Term: Tobacco use
Solid organ or blood stem cell transplantation	Excluded from trial
Tuberculosis	High Level Term: Tuberculous infections
Use of corticosteroids or other immunosuppressive medications	Excluded from trial

## 4.2. Primary Endpoint Analysis

### 4.2.1. Definition of Endpoint(s)

Serum samples will be collected from subjects per the trial procedure schedule [Appendix 1](#), Immunogenicity testing will be performed at [REDACTED], and at contracted laboratories, if needed.

Neutralizing antibody results against SARS-CoV-2 are assumed to be log-normally distributed. Values will be transformed to the  $\log_{10}$  scale for the purpose of analysis. Results that are below LLOQ or LLOD will be evaluated based on the algorithm described in Section 4.1.1. Once analyses are performed, estimates will be back transformed to the original scale for reporting.

Foreseeable intercurrent events and handling strategies are described in Section 1.1 for primary and secondary estimands.

### 4.2.2. Main Analytical Approach

The estimate of the primary estimand will be created using the IAS.

The geometric mean, 95 % CI, median, minimum, and maximum of SARS-CoV-2 neutralizing antibody results for Part A will be calculated within each cohort. Additionally, in Part A, the ratios of the GMTs between ABNCoV2 and Comirnaty will be provided along with p-values, 95% CI and 97.5% CI from a generalized linear model. Age and baseline neutralizing antibody results will be included as covariates in the model to compare between the vaccination arms. The Least Squares (LS) Means and CIs from the model will be back transformed to their original scale.

GMTs will be obtained by computing the arithmetic means and the corresponding 95% CIs on the  $\log_{10}$  scale, and then exponentiating the  $\log_{10}$  means and confidence limits to return the results to the original scale.

Figures of neutralizing antibody results with the GMT and fold increase for the index virus and each VOC will be plotted by cohort, and for both cohorts combined, for each vaccination arm in Part A.

